The general aim of this study is the development of the optimal algorithm for the management of all adnexal masses. This can be broken down into different specific objectives: 1) to study the occurrence of complications such as rupture, torsion, or malignancy in patients with benign looking conservatively treated masses; 2) to test the published IOTA diagnostic models for predicting that a mass is malignant at first visit or benign (either on the basis of histology following surgery or by the absence of malignant features on an ultrasound scan one year after the initial visit), and to predict complications (e.g. ocurrence of malignancy and other) during long-term follow-up; 3) to investigate factors that may be related to the need for surgery during long-term follow up; 4) to study the natural history of conservatively treated benign looking masses and to establish descriptive curves of the longitudinal changes seen in parameters from conservatively managed benign tumors (e.g. change in diameter, size of any solid component, number of papillations, or color score). We hope these curves will allow us to determine if any particular growth pattern is associated with complications or malignancy

Related to these four objectives, we aim to carry out the following analyses: 1) descriptive analysis of complications overall and by participating center (anonymised) and overall Kaplan-Meier curves for the need for surgery among benign looking masses; 2) estimation of discriminatory ability of LR1 for malignancy at the initial visit using the c-index and ROC curves and for complications during long-term follow-up using the hazard ratio and c-index within the context of survival analysis; 3) survival analysis to investigate predictors of the need for surgery during long-term follow-up of non-operated masses; 4) the development of longitudinal curves of the changes seen in the characteristics of non-operated masses using longitudinal analysis techniques such as mixed models and functional linear discriminant analysis (FLDA).

Methods

Study design

International multicenter prospective observational cohort study

Eligible for inclusion

- Any woman at least 18 years old with an adnexal mass.
- Any mass with benign ultrasound morphology may be suitable for conservative management.
- Pregnant patients can be included, but their data will be analysed separately.

Exclusion Criteria

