This is an observational study and therefore a sample size cannot be calculated. We aim to collect at least 3000 women with an adnexal mass and at least 1000 women with an adnexal mass managed conservatively. We plan an initial recruitment period of eighteen months. Patients will be followed up for at least 5 years, unless surgical intervention is necessary.

Follow-up

Ultrasound (and clinical) follow up will be organised by the ultrasound examiner who entered the patient into the study. Follow-up will be after 3 months (maximal range 1-4 months), 6 months (maximal range 4-8 months) and then every 12 months (maximal range 10-14 months). Although measurement of serum CA 125 levels is encouraged, it is not mandatory for inclusion in the study. If CA125 is measured it should be recorded in the study screen and preferably measured on each visit.

Duration of follow-up

A yearly analysis will be carried out in order to evaluate acute complications. The duration of follow up will be for at least 5 years and is not limited as long as the patient is compliant with the study and the study is ongoing.

Departments (e.g. radiology departments) that are not involved with clinical decision making about plans for follow up or surgery cannot participate in the full IOTA 5 study. In these centres data can be prospectively collected as an observational study. Only patients with appropriate outcome measures (i.e. follow up ultrasonography after one or more years or patients with complete details of clinical history or surgical procedures) will be included in any statistical analysis.

Collection of clinical data

Family history: Number of first degree relatives with ovarian cancer (0-...)

Medical history:	Personal history of ovarian cancer and breast cancer
	Age (years)
	Previous hysterectomy (yes/no)
	Previous oophorectomy (yes/no)
	Contraception (drop down list) (None/oral combined contraceptive
	pill/progestogen only pill/ patch/vaginal ring/Mirena coil/copper IUD)
	Hormonal therapy (yes, no).
	Is the patient currently wishing to conceive? (yes/no)
	Menopausal status (pre- or postmenopausal)
	History of subfertility? Yes/no
	History of ovarian stimulation for subfertility? Yes/no
For ALL path	ents before menopause two extra questions pop up:

Patient is currently pregnant? (No/Yes)

Patient became pregnant during the last year? (No/Yes)

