- If yes : date of first complication:

- And pop up list (you can select more than one):
 - Acute pain
 - \circ Chronic pain
 - Suspected torsion
 - o Infection
 - Haemorrhage
 - o Rupture
 - $\circ~$ Other, please specify:
- Death: date
- Death directly or indirectly relatd to adnexal mass?
- cause of death (

• Autopsy findings: specify:

Not needed for IOTA phase 5: second stage tests

Consent / information leaflet

Information leaflets are at the discretion of the participating centres. Approval of the local Ethical Committee for clinical studies is necessary.

Serum tumour markers

Serum CA 125 measurements or other tumour markers are performed locally, using a CA 125 II immunoradiometric assay

Tissue collection

Preferably the whole tumour should be removed. However, representative biopsies may be sufficient (e.g. in advanced ovarian cancer or endometrioma).

Tumour classification

Tumours are classified according to the criteria recommended by the International Federation of Gynecology and Obstetrics (FIGO). In malignant tumours the degree of differentiation is included.

Statistical analysis

For the first objective, a descriptive analysis of complications on all data and stratified for participating center (anonymized) will be performed, as well as an overall Kaplan-Meier curve of 'complication free survival'. Complication free survival is defined as the time to the need for surgery during long-term follow-up. Patients that did not need surgery at the end of the follow-up period are right censored at the time of the last examination.

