For the second objective, the discriminatory ability of LR1 and the polytomous model to detect malignancy at the initial visit will be assessed. To this end, the logit of the risk of malignancy given by LR1, logit(LR1), is used to predict malignancy using logistic regression, and the performance assessed with the odds ratio, the c-index and a ROC curve. Linearity of the effect of logit(LR1) will be assessed using spline functions. This analysis is planned one year after the end of the inclusion phase of the trial. Non-operated masses will be classified as benign at the initial visit if there is an absence of a clinical diagnosis of cancer after 1 year of follow up. In addition, the ability of LR1 to predict complications during long-term follow-up will be assessed. This will be done using Cox proportional hazards regression with the logit(LR1) as predictor of complication free survival. Performance will be assessed using the hazard ratio and the c-index within the context of survival analysis. Linearity of the effect of logit(LR1) will be investigated using Schoenfeld residuals.

For the third objective, a multivariable survival analysis will be undertaken using Cox proportional hazards regression or more complex alternatives based on support vector machines (30). The models will be penalized to prevent overfitting, given that not enough events (i.e., patients that need surgery during long term follow-up) are expected for the number of available predictor variables. Internal validation will be assessed through bootstrapping rather than a split of the data in training and test sets (31).

For the fourth objective, longitudinal normative curves will be derived of the changes seen in the characteristics of non-operated masses. Longitudinal analysis techniques such as mixed models, longitudinal support vector machines, and functional linear discriminant analysis (FLDA) (32-34).

Study supervision

Central supervision: the Steering Committee is responsible for the protocol, quality control, interim analyses of the data and final analysis and reporting of the study.

Local supervision: the Principal Investigators are responsible for the data collection in their centres.

[name] is responsible for the co-ordination of the overall IOTA project and the contact between the centres.

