1.2.2 Methods

To describe findings during follow up, we will use cumulative incidence curves that reflect the competing risk setting. The follow-up time will be computed in months.

In competing risk survival analysis, the hazard and cumulative incidence of competing (i.e. mutually exclusive) events are estimated over time. The basic competing risk outcome levels reflect the overall study outcome, and are 'surgery performed', 'cyst spontaneously resolved', and 'patient died (for any reason)', whichever comes first. When surgery is performed, this can be further subdivided based on reason for surgery and findings at surgery. For these subdivisions, it is possible that two events (i.e. reasons or findings) occur simultaneously. For example, a patient can undergo surgery due to acute pain and fertility concerns. We therefore specified a hierarchy of the competing events and if two events occur simultaneously, the event highest in the hierarchy is given to the observation. The hierarchies are shown in Box 1. For example, when the patient is operated due to acute pain and fertility concerns, the patient is said to have the event acute pain.

Box 1. Hierarchy of reasons for surgery and findings at surgery.

Reasons for surgery	Findings at surgery
1. Suspicion of malignancy ^a	1. Invasive
2. Pain ^b	2. Borderline
3. Patient request/opportunistic ^c	3. Torsion
	4. Cyst rupture
	5. Minor complications ^d
	6. No complications of tumor

^a Includes ‘suspicion of malignancy based on ultrasound; suspicion of malignancy based on: increase in size, change in morphology, change in vascularity, raised or increase in CA125, raised HE4, CT finding, MRI findings’

^b Includes ‘acute pain (suspected torsion, suspected cyst rupture), chronic pain’

^c Includes ‘fertility concerns, patient request, opportunistic removal’

^d Includes ‘tumor bleeding, adhesions, inflammation/infection’

We will derive cumulative incidence functions for study outcome, reason for surgery, and findings at surgery. For each outcome, figures depicting the cumulative incidence will be produced, as well as tables at time points 12 and 24 months containing the cumulative incidences of the competing events with 95% CI.

Median follow-up will be estimated by the reverse Kaplan-Meier method, i.e. where censoring is denoted as the event, and events denoted as censoring. This is the common method to visualize the censoring function.

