 - o If surgery was >120 days after the inclusion visit, but subjective assessment was not always probably or certainly malignant (including borderline) at every visit: classify as *uncertain (U1)*

- B. The tumor spontaneously resolved at any point during follow-up: classify as *benign*

- C. The patient did not receive surgery, the tumor did not resolve, and the last follow-up visit was ≥ 10 months after the inclusion visit:

- If subjective assessment was consistently labeled as probably or certainly benign during the first 14 months of follow-up (specific definition: subjective assessment was benign at the earliest visit after ≥ 10 months of follow-up, and subjective assessment was benign at all visits up to 14 months of follow-up): classify as *benign (B2)*
- If subjective assessment was consistently labeled as probably or certainly malignant (including borderline) during first 14 months of follow-up (specific definition: subjective assessment was borderline/malignant at the earliest visit after ≥ 10 months of follow-up, and subjective assessment was borderline/malignant at all visits up to 14 months of follow-up): classify as *malignant (M3)*
- Else, subjective assessment was inconsistent/uncertain during the first 14 months of follow-up: classify as *uncertain (U2)*

D. Other cases: classify as *uncertain*

- Patients that received follow-up of less than 10 months, without receiving surgery or experiencing spontaneous resolution of the tumor. Reasons for such short follow-up can be death, withdrawal from the study, or being lost to follow-up. (U3)
- Patients for which we did not have information after the inclusion visit. Reasons for such short follow-up can be death, withdrawal from the study, or being lost to follow-up. (U4)

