1.5 Statistical methods

1.5.1 Missing values for CA125 and outcome

CA125 was not mandatory in IOTA5, although it was highly encouraged. We expect missing values for CA125, for the following two reasons. First, following local protocols some centres were more committed than others to measure CA125. Second, the need to measure CA125 may depend on the overall clinical picture and the appearance of the tumour on ultrasound. Hence we expected clearly more missing values for cases that were followed up conservatively.

For some cases, as outlined above, the outcome is uncertain. The largest groups are cases without any information since the inclusion scan (U4 in the overview above), and cases with last FU <10 months after inclusion and without having had surgery and where the mass did not resolve spontaneously (U3).

Simply omitting cases with missing CA125 or outcome is likely to cause bias. For example, based on data from earlier IOTA studies, patients with missing CA125 have more often a benign tumor. The current data from IOTA5 indicate that CA125 is more often missing for patients that are followed conservatively than for patients that received surgery without follow-up visit. Further, we assume that conservatively followed patients with last follow-up <10 months will very often have a benign tumor.

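### Neither SAP uses cause of death, autopsy or a clinical cancer diagnosis to ascertain malignancy, so a known cancer in an unoperated woman can be counted only as a death, imputed, or labelled benign

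*SAP*

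**What the plan says.** Protocol. The first objective is "to study the occurrence of complications such as rupture, torsion, or malignancy in patients with benign looking conservatively treated masses"; it is not limited to malignancy found at operation. Under Statistical analysis, second objective, a non-operated mass counts as benign at the initial visit "if there is an absence of a clinical diagnosis of cancer after 1 year of follow up". The Objectives section gives a second standard for benign: no malignant features on ultrasound one year after the first visit. The study screen asks "Death directly or indirectly relatd to adnexal mass", and also records cause of death and autopsy findings.

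Follow-up SAP (2017), section 1.2.2. The competing events are surgery, spontaneous resolution and death from any cause. The subdivision that contains malignancy hangs on one of them: "When surgery is performed, this can be further subdivided based on reason for surgery and findings at surgery". Invasive and borderline tumours appear only in the findings-at-surgery column of Box 1. The planned listing of confirmed malignancies also has a column for surgical findings and none for any other source of diagnosis.

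Model-performance SAP (2019), section 1.3. Without surgery or resolution, rules C and D use only subjective assessment and length of follow-up. Follow-up of 10 months or more leads to B2 (benign), M3 (malignant) or U2 (uncertain). Shorter follow-up leads to U3, and no information after inclusion leads to U4. Of U3 the SAP says "Reasons for such short follow-up can be death, withdrawal from the study, or being lost to follow-up. (U3". Sections 1.5.1 and 1.5.2 treat uncertain outcomes as missing and impute them in the primary analysis.

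**The concern.** The protocol is motivated by the unknown number of cancers missed among masses left in place. A woman whose benign-looking mass proves to be cancer and who never reaches surgery is the most serious false negative of conservative management. Her cancer may be on file, in the death and autopsy fields, but no rule in either SAP reads them.

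In the 2017 analysis this can only lower the reported malignancy incidence. In the 2019 analysis a known status is replaced by an imputed or benign one. That flatters subjective assessment, and any model that gave the woman a low risk at inclusion, and it does so most in the prespecified subgroups with follow-up scans or with conservative management suggested, where malignancies are few. Subjective assessment is itself under evaluation and also defines B2 and M3. For unoperated, unresolved masses the death and diagnosis data are therefore the main independent check on it.

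**Working it through.** **Tracing the rules.** Take a woman with an unresolved mass, never operated, in whom adnexal cancer becomes known.

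| Situation | Follow-up SAP 2017 | Model-performance SAP 2019 |
|---|---|---|
| Dies of the cancer, last visit before 10 months | Death from any cause | U3 (U4 if never rescanned): imputed |
| Alive with non-operative diagnosis, last visit before 10 months | No malignancy event | U3 or U4: imputed |
| Last visit at 10 months or later, assessments benign | Death, or no malignancy event | B2: benign |
| Same, assessments mixed | Death, or no malignancy event | U2: imputed |
| Same, assessments consistently borderline or malignant | Death, or no malignancy event | M3: malignant |

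The 2017 column assumes at least one follow-up scan, which that survival analysis requires. Only the M3 row keeps the cancer as a cancer.

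**Does imputation recover it?** The predictor list in 2019 section 1.5.1 holds inclusion-scan features, age, history, symptoms, centre type and CA125. It has no death, cause of death, autopsy or later diagnosis. A woman who looked malignant at inclusion can be imputed malignant; one who looked benign will mostly be imputed benign.

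**Do the sensitivity analyses recover it?** Section 1.5.8 has one analysis that excludes U1 to U4 and one that re-imputes them together with the groups labelled by subjective assessment, including B2. Neither uses the recorded evidence.

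**Size.** The plan has no figure to reproduce: it states no expected event count, and the protocol says "This is an observational study and therefore a sample size cannot be calculated". What follows is illustration.

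- *Denominator.* From the presumed-diagnosis table in 2017 section 1.2.2, 1470/0.47 = 3,128. Requiring every printed percentage to agree with its count after rounding gives a lower limit from 609/0.195 = 3,123.1 and an upper limit from 1470/0.465 = 3,161.3, so N is 3,124 to 3,161.
- *Absolute shift per uncounted cancer,* 1/N: 1/3,124 and 1/3,161 are both about 0.03 percentage points. At the protocol minimum of "at least 1000 women with an adnexal mass managed conservatively" it is 1/1,000 = 0.1 points.
- *Share of all malignancies missed,* k/(s + k), with s found at surgery and k uncounted (both assumed):

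| s | k = 1 | k = 3 |
|---|---|---|
| 5 | 1/6 = 17% | 3/8 = 38% |
| 10 | 1/11 = 9% | 3/13 = 23% |
| 20 | 1/21 = 5% | 3/23 = 13% |

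- *Sensitivity in the 2019 analysis,* M × se/(M + q × k), where M is the other malignancies, se the sensitivity among them, k the non-operative cancers (all below the cut-off at inclusion) and q the probability that each is treated as malignant. Compare q = 0.1 (imputed) with q = 1 (counted), for k = 5; all values are assumed.
  - M = 20, se = 80%: 16/20.5 = 78.0% against 16/25 = 64.0%.
  - M = 500, se = 90%: 450/500.5 = 89.9% against 450/505 = 89.1%.

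**The case against.** A reader might infer that these women drop out of both analyses. The documents do not support that. In the 2019 primary analysis U1 to U4 stay in through imputation and are removed in only one sensitivity analysis. M3 keeps some unoperated women malignant. In the 2017 analysis a missed cancer later found at operation is still counted.

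A reader might also take B2 as a plain departure from protocol. It is not: it closely follows the one-year ultrasound standard in the protocol's Objectives, and it is stress-tested by re-imputation. The conflict is narrower. When cancer was diagnosed within the year although the scans looked benign, B2 contradicts the clinical-diagnosis standard in the protocol's Statistical analysis section.

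Nor is the SAP's remark that "we assume that conservatively followed patients with last follow-up <10 months will very often have a benign tumor" an input to the imputation. It is part of the argument against simply omitting such patients.

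Three further points stand in full. The form lists primary chemotherapy under type of operation, beside a histology field, so some non-operative cancers may enter the surgery branch, although the SAPs do not say how these are analysed. The form shows no dedicated field for a non-operative diagnosis in a living woman, so talk of recorded evidence is secure only for the death and autopsy fields. And labelling every such cancer within a year as malignant at inclusion would clash with rule A, under which malignant histology after 120 days is uncertain (U1) unless every assessment was malignant. None of this explains leaving the death data unread.

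**Conclusion.** The point holds in this limited form. Neither SAP uses relation of death to the mass, cause of death, autopsy or a clinical cancer diagnosis to ascertain malignancy. Followed as written, the 2017 analysis counts an unoperated adnexal-cancer death only as a death and gives a living unoperated case no malignancy event; the resulting bias in malignancy incidence runs one way, downwards. The 2019 analysis keeps the woman but, unless she meets M3, imputes her status without the relevant information or labels her benign. A benign label for a cancer that first arises well after the assessment window can be legitimate, since that analysis concerns status at inclusion.

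The size cannot be determined from the documents. The number of women affected may be zero, and the counts used above are assumptions. The absolute effect per woman is small. The relative effect on a rare endpoint, and on sensitivity in a follow-up subgroup with few malignancies, could be large; in the full 2019 dataset, if malignancies number in the hundreds, it would be under one percentage point. The presumed-diagnosis total is not shown to be the newly-detected-mass population, where the denominator would be smaller. The correction is still worth making, because the rule overwrites known information and the remedy is cheap.

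**What to change.** 1. *Follow-up SAP 1.2.2.* Count death from adnexal cancer, and any documented non-operative adnexal cancer diagnosis, as malignancy. Split deaths into related and unrelated to the mass. List these women in the table of confirmed malignancies, with the source of the diagnosis.
2. *Model-performance SAP 1.3.* Before rules C and D, check the death, autopsy and free-text fields. Do not assign B2 when adnexal cancer is documented within the protocol's one-year horizon. For documented non-operative cancer, use a time rule consistent with rule A: malignant at inclusion when documented within 120 days, otherwise the treatment given to U1. Add a sensitivity analysis that counts all documented cancers within one year as malignant. For women classified malignant, impute only the malignant subtype, and only where it is unknown. State how cases entered as primary chemotherapy are handled.
3. *Both.* Report how many women are affected, even if none.

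The cost is SAP wording and a check of fields already collected for deaths. Living non-operative diagnoses may need a query to centres, because the form shows no dedicated field. A few labels would rest on non-histological evidence.
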